2 PURPOSE OF THE ANALYSES

This statistical analysis plan (SAP) contains detailed information about statistical analyses to be performed to assess the efficacy and safety of vaginal hysterectomy with native tissue vault suspension and mesh hysteropexy suspension in women experiencing uterovaginal prolapse. The results of these analyses will be included in the primary manuscript and a series of pre-planned secondary manuscripts and be provided to Boston Scientific Corporation for a report on the efficacy and safety of mesh-associated surgery required by the FDA under a 522 letter request. Added exploratory analyses may be performed to support further manuscript development. These analyses will not require an update to the SAP.

3 STUDY OBJECTIVES AND OUTCOMES

3.1 Study Objectives

3.1.1 Primary Objectives

The primary purpose of this randomized clinical trial is to compare the effectiveness and safety of two transvaginal apical suspension strategies for uterovaginal prolapse: a mesh augmented hysteropexy vs. vaginal hysterectomy and uterosacral ligament suspension. The primary aim for this trial is to determine whether treatment success in women with symptomatic uterovaginal prolapse undergoing transvaginal mesh augmented hysteropexy differs in women undergoing vaginal hysterectomy and native tissue cuff suspension at time points through 3 years. This study will test the null hypothesis that treatment success will not differ in women with symptomatic uterovaginal prolapse undergoing vaginal surgery with a synthetic mesh hysteropexy compared to women undergoing vaginal hysterectomy with native tissue vaginal suspension against the alternative hypothesis that success does differ for the treatment regimens. Operationally, the hypothesis will be tested using a two-sided log-rank test to test for a difference in the risk of failure across the two treatment arms at a 0.05 level of significance.

3.1.2 Secondary Objectives

The secondary aims for the SUPeR study, which will be addressed through specific planned secondary analyses and associated hypothesis tests and treatment effect estimates, are:

- 1. Secondary Efficacy Outcomes: To compare detailed anatomic and comprehensive functional outcomes (including prolapse, urinary, sexual, bowel and health related quality of life (HRQOL) in both groups.
- 2. Safety: To measure and compare safety, adverse events (including mesh erosion and exposure), pain, and need for subsequent procedures in both groups.
- 3. Predictors of poor outcomes: To determine if advanced prolapse, age, obesity, smoking, menopausal status, estrogens, previous prolapse surgery, and physical activity levels, alone or in combination, predict higher treatment failure.
- 4. Cost- effectiveness: To compare the cost effectiveness of the two surgical approaches and relate the difference in cost of care between the two groups to differences in health utilities and health–related quality of life.
- 5. Body image: To describe changes in body image as measured by a validated scale, the Body Image Scale (BIS). in a group of women undergoing mesh augmented hysteropexy or vaginal hysterectomy and to evaluate whether or not changes in sexual function are associated with changes in body image.

3.2 Outcomes

The **primary outcome** for the study is treatment failure at any point after the participant leaves the operating room; note that per protocol requirements, the patient cannot leave the operating room

as a treatment failure. A participant will be considered a treatment failure if any ONE of the following criteria is met:

- 1) Report of bothersome vaginal bulge symptoms (see definition below), or
- 2) Re-treatment for prolapse (surgery or pessary), or
- 3) Any prolapse measure (Ba, C, Bp) is beyond the hymen (i.e. >0 cm)

Bothersome vaginal bulge symptoms = positive response to Question 3 of the PFDI-20: Do you usually have a bulge or something falling out that you can see or feel in your vaginal area? AND any degree of bother. This single question has been identified to most accurately and reliably identify those women with POP. An affirmative answer to this question was 96% sensitive (95%CI 92-100) and 79% specific (95%CI 77-92) for prolapse beyond the hymen. The 1-week test-retest reliability was good (kappa .84).

Participants not considered a treatment failure for the primary outcome will be considered a treatment success.

A number of secondary outcome measures will be used to support the analyses for the secondary aims listed earlier. Outcomes that will be used in the planned analyses associated with each of the secondary aims include:

- 1. Anatomical measures of treatment efficacy in the two treatment arms obtained at 6-month intervals after surgery:
 - a. Mean and median POPQ point (Ba, Bp, C) location measures postoperatively in the two treatment arms.
 - b. Proportion of participants in each group with C > -1/2 TVL
- 2. Functional measures of treatment efficacy in the two treatment arms as obtained from the measurement at 6 weeks as well as those at 6 months post-surgery and every subsequent 6-month time period through 5 years post surgery:
 - a. Participant impression of overall prolapse improvement at 6-month post-operative intervals as measured by Patients Global Impression of Improvement (PGI-I),
 - b. Mean overall prolapse symptoms at 6-month post-operative intervals based on POPDI-6 scores.
 - c. Duration of postoperative catheterization.
 - d. Urinary function measured at 6-month post-operative time points using:
 - i. Mean UDI-6 scores
 - ii. Hunskaar Incontinence Severity Index
 - iii. Risk of de novo voiding dysfunction
 - iv. Risk of de novo incontinence
 - e. Sexual functional measures obtained at 6-month post-operative time points including:
 - i. PISQ-IR scale measures
 - ii. Risk of de novo dyspareunia
 - f. Bowel function obtained at 6-month post-operative time points using CRADI-8 scores

- g. Quality of Life (QO)L measures obtained at 6-month post-operative time points including:
 - i. General SF-12 physical component and mental component scales
 - ii. Pelvic QOL as measured by PFIQ total score and three subscales
 - iii. Functional activity as measured by the Activity Assessment Scale
- 3. Safety and tolerability of the two treatment regimens:
 - a. Intraoperative safety measured in each of the treatment arms including:
 - i. Operative time
 - ii. Estimated blood loss
 - iii. Proportion of participants with blood transfusion
 - iv. Intra- and post-operative complications categorized using a modification of the Dindo Classification.
 - b. Risk of adverse events on the two treatment arms as measured by proportion of participants with any of the following events:
 - Mesh related complications: mesh exposure in the vagina or mesh erosion into another organ; note that level of complication will be characterized into based on the following response classification schema: (a) None or nonsurgical medical intervention only; (b) Minor or intra-office surgical intervention; (c) Outpatient surgery; (d) Inpatient surgery
 - ii. Rates of pain captured from the modified Surgical Pain Scale, pain medication use, and location of pain with Pain Mapping Instrument.
 - iii. Pelvic infection
 - iv. Risk of perioperative infections
 - v. Risk of urinary tract infections
 - vi. Vaginal infections with flora uncommon to the vaginal canal
 - vii. Risk of any of De novo vaginal bleeding, atypical vaginal discharge, fistula formation, neuromuscular problems (including groin and leg pain)
 - viii. Need for subsequent procedures- Any surgical or non-surgical treatment for pelvic floor disorders (including urinary incontinence, voiding dysfunction, defecatory dysfunction or fecal incontinence, recurrent prolapse, and dyspareunia/pelvic pain). Any subsequent uterine or cervical office or Operating Room procedure in hysteropexy group (e.g., cervical biopsy, LEEP, hysteroscopy, D and C, hysterectomy).
 - ix. Subsequent uterine or cervical pathology
 - x. Risk of vaginal scarring defined as: De novo vaginal scar requiring medical or surgical intervention, or adversely affecting quality of life.
 - xi. Risk of Vaginal shortening, de novo dyspareunia, and
 - xii. Risk of worsening dyspareunia with AE survey instrument.

- c. Risk of important complications in each of the two arms at any point postoperatively. Important complications are defined as:
 - i. Any Grade IIIb or greater Dindo complication, which will also include any intervention under a regional anesthetic. These concurrent or subsequent Operating Room interventions include but are not limited to: mesh removal, ureteral repair, abscess drainage, revision of vaginal stricture, operative hysteroscopy, or hysterectomy.
 - ii. New onset (de novo) dyspareunia preventing vaginal intercourse
- d. Intractable pelvic pain defined as daily pelvic pain after the 6-week postoperative visit which significantly affects the participant's quality of life requiring ongoing management or is refractory to medical and physical therapy.
- 4. Key predictors of poor treatment outcomes defined as the effect of advanced prolapse, age, obesity, smoking, menopausal status, estrogens, primary vs. recurrent prolapse, and physical and functional activity as measured by the Functional Activity Scale on higher risk of treatment failure.
- 5. Cost-effectiveness of the two treatment regimens
 - a. Clinical costs associated with participant's use of medical and non-medical resources related to urologic or gynecologic conditions will be collected during the follow up period. Direct and indirect costs of the treatment of apical pelvic organ prolapse with native tissue surgical repair or transvaginal mesh repair and women's preference for health states for improvement in pelvic organ prolapse will be estimated.
 - b. Preference-based utility index determined from SF-6D.
- 6. Body image as measured by the Body Image Scale at 6-month post-operative intervals.

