 - b) Urinary – urinary function including duration of post-op catheterization, mean UDI-6 scores⁴⁹, Hunskar Incontinence Severity Index, de novo voiding dysfunction rates, de novo incontinence rates
 - (i) Sexual – mean PISQ-IR⁵⁰ and specific rates of de novo dyspareunia
 - (ii) Bowel – bowel function using CRADI-8 scores⁴⁹
 - (iii) QOL – general SF-12 scores and sub-scales⁵¹, and Pelvic QOL mean PFIQ score⁴⁹; Functional Activity Assessment Scale⁴²

Secondary Aim 2 – Safety: These measures will require a statistical analysis plan and will be reported in the primary outcome manuscript.

- 1) Intraoperative safety – group comparisons of mean Operative time, estimated blood loss, blood transfusion, intra- and post-operative complications categorized using a modification of the Dindo Classification.⁵²
- 2) Adverse events – mesh related complications: mesh exposure in the vagina or mesh erosion into another organ and the classification of the intervention:
 - a) none or non-surgical medical intervention only

Confidential Please Do Not Copy

- b) minor or intra-office surgical intervention
- c) outpatient surgery
- d) inpatient surgery

Other complications possible in both arms:

- 1) Rates of pain captured from the modified Surgical Pain Scale⁴³, pain medication use, and location of pain with Pain Mapping Instrument
- 2) Pelvic infection:
 - a) perioperative infections
 - b) urinary tract infections
 - c) vaginal infections with flora uncommon to the vaginal canal
- 3) Vaginal shortening, de novo vaginal bleeding, atypical vaginal discharge, fistula formation, neuromuscular problems (including groin and leg pain)
- 4) Need for subsequent procedures – any surgical or non-surgical treatment for pelvic floor disorders (including urinary incontinence, voiding dysfunction, defecatory dysfunction or fecal incontinence, recurrent prolapse, and dyspareunia/pelvic pain). Any subsequent uterine or cervical office or Operating Room procedure in hysteropexy group (e.g., cervical biopsy, LEEP, hysteroscopy, D and C, hysterectomy).
- 5) Subsequent uterine or cervical pathology
- 6) Rates of vaginal scarring defined as de novo vaginal scar requiring medical or surgical intervention or adversely affecting quality of life
- 7) Rates of vaginal shortening, de novo dyspareunia, and worsening dyspareunia with AE survey instrument

Complication Monitoring

Groups will be compared for rates of “important complications”. The definition of “important complication” is:

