- Any Grade IIIb or greater Dindo complication, which will also include any intervention under a regional anesthetic. These concurrent or subsequent Operating Room interventions include but are not limited to: mesh removal, ureteral repair, abscess drainage, revision of vaginal stricture, operative hysteroscopy, or hysterectomy.
- New onset (de novo) dyspareunia preventing vaginal intercourse.

Confidential Please Do Not Copy

- Intractable pelvic pain – defined as daily pelvic pain after the 6 week postoperative visit which significantly affects the participant's quality of life requiring ongoing management or is refractory to medical and physical therapy.

The important complication rate will be calculated at 6 month intervals for both groups; as a guideline, the protocol committee considers that a true difference of more than 15 percentage points in the complication rates for the two surgical procedures to represent an important difference between groups. Stopping the study will be considered by the DSMB during their regularly scheduled reviews if they find compelling evidence of an important difference based on point and interval estimates of the important complication rates in the two study arms. While the true difference of 15 percentage points or greater can guide the DSMB considerations, final decisions about a magnitude of difference in safety risk that warrants a recommendation to stop the study lie fully within the discretion of the DSMB.

Secondary Aim 3 – Predictors of Poor Outcomes: The co-variables of advanced prolapse, age, obesity, smoking, menopausal status, estrogens, primary vs. recurrent prolapse, and physical and functional activity as measured by the Functional Activity Scale will be evaluated to determine if they predict higher treatment failure.

Secondary Aim 4 – Cost-Effectiveness Analysis: The cost-effectiveness analysis will be conducted from a payer perspective and will be expressed as incremental cost required to produce one additional unit of quality-adjusted life year (QALY). Data on each participant's use of medical and non-medical resources related to urologic or gynecologic conditions will be collected during the follow up period. Direct and indirect costs of the treatment of apical pelvic organ prolapse with native tissue surgical repair or transvaginal mesh repair and women's preference for health states for improvement in pelvic organ prolapse will be estimated.

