7.4 Interim Analyses and Data Monitoring

A single planned interim analysis is planned with the last randomized participant reaches the 24month follow-up exam. The purpose of the interim analysis is to stop for benefit. Stopping boundaries will generated using Lan-DeMets alpha spending functions with the O'Brien-Fleming type approach. The alpha level for the interim analysis is expected to be about 0.003 and to allow for this interim look, the final test will be conducted at the 0.047 level of significance.

The DSMB will also review enrollment data and safety data at 3-month intervals and will have the responsibility of recommending to the Director of NICHD that the study be stopped for safety or futility. Each of these issues is addressed in the paragraphs below.

The interim safety analyses conducted by the DSMB will be conducted based on a review of any study deaths (note that the number of deaths in the population under study is expected to be minimal) and important complications as defined in Section 3.2. The important complication rate will be

calculated at 6 month intervals for both groups; the protocol committee considers that a true difference of more than 15 percentage points in the complication rates for the two surgical procedures to represent an important difference between groups. Stopping the study will be considered by the DSMB during their six-month reviews if they find compelling evidence based on point and interval estimates of the important complication rates in the two study arms that the true difference is 15 percentage points or greater. The DSMB is charged with determining the level of evidence that they consider compelling for stopping the study for safety reasons.

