10.2 Adverse Events

As described in Section 3.2, four types of measures will be utilized to characterize participant safety and tolerability measures. First, as a part of the inter-operative and peri-operative data collection forms, information will be collected on surgical complications that characterize the risk and tolerability of the procedure itself. Second, participants will be asked about specific targeted complications on both the post-operative visit and a standard study evaluation collected at 6-month intervals (with those complications automatically populating the AE form. Third, participants will be asked through a response to open-ended questions to report any post-surgery adverse events to the study coordinator or physician at the 6-week visit and at the subsequent follow-up visits at 6-month intervals. If a serious adverse event, particularly a hospitalization, occurs, the participants will be asked to report that immediately to the study coordinator or physician. All adverse events are captured by the study coordinator on the adverse event logs. Finally, specific pain information is being collected as a part of all follow-up visits to characterize differences in post-operative pain beyond 6 weeks.

The group of measures collected inter-operatively and peri-operatively includes those in the table below. These measures include continuous measures as well binary and ordinal measures. For the

continuous measures, summaries will be presented by treatment arm that include mean levels and standard deviations and linear models with treatment as the primary predictor, controlling for site will be used to test for differences by treatment arm. For the binary and ordinal measures, summaries will included counts and percentages associated with each level of the binary or ordinal measure and Cochran-Mantel-Haenszel statistics and associated p-value with analyses stratified by site will be used to characterize differences in the treatment arms.

The AEs collected through the standard AE form will be summarized using standard contingency tables by treatment arm. These summaries will be provided by individual treatment-emergent AEs, AEs by body system, and AEs by subject. In addition to these general descriptions, specific comparison of risk and differences across the treatment arms will be evaluated for the outcomes listed in the table below.

Summary of Safety V	ariables				
Inter-operative and peri-operative measures					
Variable	Туре	Definition			

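### The SAP's important-complication composite has two of the protocol's three components, and neither the composite nor intractable pelvic pain has a specified arm comparison

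*SAP*

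**What the plan says.** **Protocol, Section M.2, Complication Monitoring.** The composite is an arm comparison: "Groups will be compared for rates of" important complications. Its definition is three parallel bullets:

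- "Any Grade IIIb or greater Dindo complication, which will also include any intervention under a regional anesthetic"
- "New onset (de novo) dyspareunia preventing vaginal intercourse"
- intractable pelvic pain, "defined as daily pelvic pain after the 6 week postoperative visit which significantly affects" quality of life and needs ongoing management or is refractory to treatment.

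The rate is to be calculated every 6 months in both groups. A true difference above 15 percentage points is offered to the DSMB as a guideline.

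**SAP 3.2.** Item 3c (important complications) has two sub-items, the Dindo and dyspareunia components. The third protocol bullet appears one level up, as item 3d: "Intractable pelvic pain defined as daily pelvic pain after the 6-week postoperative visit".

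**SAP 7.4.** DSMB safety review rests on deaths and on "important complications as defined in Section 3.2", with the 15-point figure repeated.

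**SAP 10.2.** For adverse events, "specific comparison of risk and differences across the treatment arms will be evaluated for the outcomes listed in the table below". That table has no row for important complications or for intractable pelvic pain.

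**SAP 14**, where departures from the protocol would be recorded, is left to be completed later.

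**The concern.** A programmer who follows SAP 3.2 literally would build a protocol-defined safety composite from two of its three components. A programmer who follows SAP 10.2 literally would not compare the composite between arms at all.

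This matters because of what the measure is for. Protocol Section P.2 lists pelvic pain with erosion and dyspareunia among the mesh risks in the FDA warning. Section M.2 says the safety measures need a statistical analysis plan and belong in the primary manuscript. SAP Section 2 sends the results to the device manufacturer for an FDA-required report on the efficacy and safety of mesh surgery. The protocol's extension amendment says later analyses will use methods consistent with those at 3 and 5 years, so a wrong definition could carry forward.

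**Working it through.** The documents give no event rate, power or sample size for this composite, so there is no figure to reproduce. The check is a comparison of the texts.

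**1. Components of the composite**

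| Component | Protocol M.2 | SAP 3.2 item 3c |
|---|---|---|
| Dindo IIIb or greater | yes | yes (i) |
| De novo dyspareunia preventing intercourse | yes | yes (ii) |
| Intractable pelvic pain | yes | no; separate item 3d |
| Count | 3 | 2 |

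The guideline is 15 points in both documents.

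**2. Specified arm comparison in SAP 10.2**

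| Quantity | Nearest row | Does it match? |
|---|---|---|
| Composite | none | no |
| Dindo component | Complications, by worst Dindo score | listed under inter- and peri-operative measures; item 3c covers any time postoperatively |
| Dyspareunia component | Dyspareunia | counts all incidents whether or not de novo, with no requirement that intercourse is prevented |
| Intractable pelvic pain | none | no |

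The shells in SAP 17 do not fill the gap. They cover perioperative outcomes, six-week outcomes and overall AE counts. The third component begins only after the six-week visit, so a six-week table cannot hold it. Pain scale score appears only in the baseline shell.

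**3. What leaving out one component does**

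Let p be the proportion with a Dindo or dyspareunia component, q the proportion whose only component is intractable pain, M the mesh arm and N the native tissue arm.

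- SAP difference: D2 = pM − pN
- Protocol difference: D3 = (pM + qM) − (pN + qN)
- Shift: D3 − D2 = qM − qN

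The shift depends only on pain-only events, and it takes the sign of their difference. The documents give neither q.

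**4. Illustration with assumed rates only**

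Arm sizes are 88 and 87, from the SAP shells. Intervals are Wald: D ± 1.96 × √[rM(1 − rM)/88 + rN(1 − rN)/87], where r is p for the two-part composite and p + q for the three-part composite.

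| Assumed p, M vs N | Assumed q, M vs N | D2, points (95% CI) | D3, points (95% CI) |
|---|---|---|---|
| 20% vs 10% | 2% vs 1% | 10.0 (−0.5 to 20.5) | 11.0 (0.1 to 21.9) |
| 20% vs 10% | 5% vs 1% | 10.0 (−0.5 to 20.5) | 14.0 (2.8 to 25.2) |
| 20% vs 10% | 8% vs 2% | 10.0 (−0.5 to 20.5) | 16.0 (4.4 to 27.6) |
| 10% vs 10% | 5% vs 1% | 0.0 (−8.9 to 8.9) | 4.0 (−5.9 to 13.9) |

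If the pain-only excess lay in the other arm, say 1% vs 5% with p at 20% vs 10%, then D3 = 21 − 15 = 6 points against D2 = 10. The omission would then widen the apparent gap. In every tabulated case the interval half-width (about 9 to 12 points) exceeds the shift (1 to 6 points).

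**The case against.** **It may be a numbering slip.** Item 3d follows directly after 3c.ii, repeats the protocol's third bullet almost word for word, and lacks the outcome wording of 3c. The same list flattens the infections that the protocol nests under pelvic infection, and some of this may come from how the PDF was read. This is plausible and stands as an explanation. It does not settle what the composite is, and renumbering would not supply the missing 10.2 rows.

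**A reader might infer that pelvic pain has dropped out of the safety analysis.** The documents do not support that. Pain rates from the Surgical Pain Scale, medication use and pain mapping are in 3.2 item 3b.ii, and intractable pain is itself a named outcome in 3d. SAP 10.2 makes pain information one of its four types of safety measure, and 10.4 tabulates all AEs by arm. Pain leading to an operating-room or regional-anaesthetic intervention still counts through Dindo IIIb. What is missing is narrower: none of these places gives a variable, source form and test for intractable pain as defined.

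**A reader might infer that the DSMB monitored the wrong rate and could have missed the 15-point mark.** That is not shown. The SAP shells carry the label Version 1.0, 12/15/2018. SAP Section 1 says the interim results had already been reviewed and the study continued, and the first data lock in SAP 4.4.2 was tied to 16 February 2018. The protocol held the three-part definition throughout. Its 15 points are a guideline, and the decision is left to the DSMB.

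**Safety p-values are descriptive, and displays may be added without amendment** (SAP 7.7 and 16). Both are true, and the primary endpoint and its error control are untouched. But SAP 16 allows such additions only if they do not contradict the SAP text, and a three-part composite would contradict 3.2 as printed.

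**Conclusion.** The concern holds as a mismatch between protocol and SAP plus an unspecified analysis. The composite has three components in the protocol and two in the SAP, with the guideline figure unchanged and no change declared. Neither the composite nor intractable pelvic pain has an arm comparison specified in SAP 10.2, and the two retained components are not compared there as the composite defines them.

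The clear effect is on the final safety report. Its size and direction cannot be stated. It is tempting to subtract an assumed pain excess of 2 to 5 points from 15 and say that a true 15-point gap would show as 10 to 13. That needs rates the documents do not give, no overlap with the other components, and an excess in the arm that is already worse. The mismatch does not depend on any of these.

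**What to change.** 1. In SAP 3.2, make intractable pelvic pain item 3c.iii, so that the composite matches Protocol M.2. The cross-reference in SAP 7.4 then needs no edit.
2. In the SAP 10.2 table, add rows for the three-part composite and for each component as defined: Dindo IIIb or greater at any time postoperatively, de novo dyspareunia preventing intercourse, and intractable pelvic pain. Name the source form for each, and add matching display shells.
3. Compare these rows by arm with the methods in SAP 10.1: Fisher exact if events are rare, Cochran-Mantel-Haenszel otherwise.
4. If the Surgical Pain Scale is compared, use a longitudinal model at its scheduled visits (6 weeks, then 6, 12, 18, 24, 36, 48 and 60 months). The site-stratified Cochran-Mantel-Haenszel method in 10.2 is stated for peri-operative binary and ordinal measures and does not suit a repeated scale.

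The cost is mainly SAP wording and a few table rows. One point needs checking first. Pain data are collected at follow-up, but the documents identify no form item that captures the full definition (daily pain after six weeks, effect on quality of life, and ongoing management or refractoriness), so the source must be confirmed.
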